Data collection will be conducted at the Northampton VA Medical Center and the West Haven VA Medical Center. Veterans will complete baseline evaluations, and then be given a user ID and instructions to log-on to a study website at home to receive their randomization assignment. Only those who do so will continue in the study and be asked to complete the telephone-delivered assessments on weeks 4, 12, and 24. This randomization after logging in restricts participation to people who demonstrate some motivation and ability to access a website.

Sequence of procedures for the clinical trial:

- Potentially eligible Veterans scheduled for a Compensation examination are identified by reviewing Compensation clinic schedules and charts.
- Potentially eligible Veteran receives letter explaining that a study recruitment telephone call will be coming, thus allowing the Veteran to opt out of receiving it (see Appendix). Veterans can also opt out by calling a toll-free phone provided in the letter.
- Telephone call inviting participation. The Research Assistant calls and asks the Veteran questions to determine eligibility. Following a script (see Appendix), the Research Assistant describes the study to the Veteran and schedules an appointment for informed consent and data collection. Appointments will be scheduled before a Veteran's planned Compensation examination and up to 3 months after the exam. Veterans vary in how able they are to schedule appointments immediately before or after Compensation examinations. Flexible scheduling balances feasibility and experimental rigor.
- Informed consent and baseline data collection by Research Assistant.
- The Research Assistant gives the Veteran a user ID and password to log on to the study Website.
- Veteran goes home, logs onto the website, and receives directions to log-on to either the Benefits Counseling or Control websites (i.e. the Veteran is randomized).
- Veteran is called by the study therapist within two days of logging on and is counseled with the assigned treatment. If the Veteran has not logged on for randomization within a week, then the therapist will call and encourage the Veteran to log-on for randomization and continuation in the study. If after one more week the Veteran has not been randomized, that participant will be discontinued from the study.
- Assessments by phone at weeks 4, 12, 24 (only of randomized Veterans).

B. Remotely-Delivered Benefits Counseling

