2. *Feasibility of Randomizing 130 Veterans*: A review of Compensation examinations conducted at Northampton over a 12 month period showed that 547 were conducted for psychiatric conditions. Of these, 348 were initial examinations, 190 were reviews, and 9 were for other reasons. We are estimating that approximately 60% of the 348 will be working fewer than two days per week and receiving less than 30% service-connection. In a chart review of Compensation examinations conducted at our MIRECC site in Bedford, approximately half (17 out of 38) of Veterans coming for new psychiatric Compensation evaluations were both not working *at all* and less than 30% service-connected. Some Veterans will be excluded for other reasons. Therefore, we estimate that 209 eligible Veterans will be approached in a year, which is enough to randomize 130 over two and a half years of recruitment.

3. Balancing the study groups: Participants will be randomized by the Project Director, with assignment delivered by the website, using an urn randomization procedure [52] that offers the benefits of balancing allocation of important prognostic variables in treatment groups, while still retaining other benefits of random assignment. The factors in the urn will be those potentially related to vocational outcomes in Veterans:

- Self-reported use of an illicit drug and/or risky alcohol use within the past 3 months (as measured by the ASSIST, using standard definitions [53,60,61,62]) within the last 28 days. Opioid use will qualify if the opioids were *not* prescribed to the Veteran.
- Current enrollment in VA psychiatric or substance abuse treatment (yes/no).
- Race (African American –yes/no) has been associated with responses to remotely-delivered behavioral messages [54].

Justification for Why Follow-up Data Collection after Baseline will be Done via Telephone:

Timeline followbacks have been administered by phone for substance abuse evaluation and are highly consistent with face-to- face assessments conducted in the same participants---in fact reports of substance use were numerically higher with the telephone assessment, suggesting a greater likelihood of truthful reporting of embarrassing information by phone [55]. The follow-up assessments are also relatively brief, taking 30 minutes or less per session. Veterans will have already completed these assessments at the face-to-face baseline visit so they will be familiar with them when they are re-administered by phone.

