BL, 4, 12, 24	Potential Mediators	Work-Related Attitudes Scale: Work Importance and Confidence Ruler
Therapy Session	Process	Audio-recorded Phone Calls
Week 8, 24	Process	Satisfaction with Counseling and with Websites (mailed assessment)
End-of-Study	Process	Extent of Study Participation from Therapist Cell-Phone (# minutes on phone with Therapist) Extent of Benefits Counseling Website Use (# days logged on to website, # modules completed)
End-of-Study	Extract Data from C&P Exam and VA Database	Mental Health Diagnoses and service connection outcome and award determination from C&P Examination Reports and VBA databases and VA Mental Health Service Use from VA Databases

Justification for Schedule of Assessments: The initial 4-week assessment follow-up date was chosen because results of Motivational Interviewing interventions have been detectable this quickly in other studies [56]. In our randomized clinical trial of in-person Benefits Counseling, week 24 assessments allowed for detection of later emerging effects of Benefits Counseling.

Baseline Assessment Measures to Characterize Participants: The following measures will be administered by the Research Assistant in a face-to-face meeting prior to beginning the intervention:

1. Baseline Characteristics Questionnaire: A questionnaire to characterize study participants has been used in our recently-completed Benefits Counseling study. It covers the following domains: demographics, military history, psychiatric history, employment, legal status, and last 28 days of income by source. It also includes 10 items from the Attitudes toward Seeking Professional Psychological Help Scale-Short Form [57]. This widely-used scale consists of two factors, one reflecting openness to seeking treatment for emotional problems and the other reflecting value of seeking treatment and need for it. The Questionnaire also includes a four-question screen for TBI, a screen which is intended to be sensitive but not specific, when a single positive answer is interpreted as a positive screen [58]. Internet usage is measured using items derived from a clinical trial of an interactive voice response system [59]. Veterans are asked whether they own different technology types (e.g. a working cell phone), whether they make different uses of it (e-mail, text messaging, searching) and number of days engaged in activities such as sending e-mail.

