does not record how long was spent on the website because it cannot distinguish between when someone is using the program, has left the browser open, or has left the program without logging out. Study therapists will complete a contact log for each encounter. The contact log will document whether there was a scheduled contact that was not attended, the date and time of contact, and time spent in minutes.

End of Study Measures

1. The current diagnoses, service-connection outcome, and award determination will be obtained from the completed Compensation and Pension examination and VBA database. Diagnoses will be coded within DSM-V with specifiers for definite diagnoses and rule-outs.
2. VA Service Use Outcomes. Analyses will be conducted by [name], a national authority on service use analyses. Episodes reflecting use of VA substance abuse, specialized PTSD and other mental health treatment will be collected from VA administrative records as described previously [73, 74]. Information will be accessed by an agreement between the MIRECC and the West Haven-sited Northeast Program Evaluation Center (NEPEC), which routinely accesses this information for VA reports. VA bed section codes indicate hospitalization on specialized units and VA clinic codes indicate outpatient treatment in specialized clinics. Mental Health service use data will be collected from 24 weeks before the Compensation examination (to allow analyses to control for baseline service use) until 24 weeks after claims adjudication.
3. Cost of Therapist Time Providing the Intervention: The direct costs of providing Remotely-Delivered Benefits Counseling will be calculated but a full cost-effectiveness analysis is beyond the scope of this proposal. The amount of time the therapist spends will be calculated by having therapists maintain logs of time spent on study-related activities including conducting telephone calls, scheduling phone calls, and reminding Veterans to access the study website. The product of the therapist's time spent and the average therapist cost will be used to calculate the labor cost. Therapist salaries will be calculated including fringe benefits but not the overhead rate of the VA facilities. We will not include research costs, facility costs, or the costs of developing the intervention.

Data Analysis

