Justification for recruitment via mailed letter: The proposed letter recruitment strategy, which was used in several of [name] other approved studies including two SBIRT studies (projects which deliver SBIRT to Veterans applying for disability for painful musculoskeletal conditions or PTSD) and the QUERI study (a multi-site study of the Compensation and Pension process directed by [name]), was effective. The main reason for recruitment by letter is that it would not be feasible to recruit Veterans at the time they come for their Compensation examination because Veterans may not have time to consider study participation when they are already at their Compensation examinations. Veterans at their Compensation and Pension evaluations may be nervous and rushed. They may be accompanied by other people who cannot or will not wait while the Veteran participates in an unplanned study. Additionally, assessments are designed to be collected before the Compensation examination.

A second mode of recruitment will involve having C&P clinic staff (but not the C&P examiner) give potentially eligible Veterans a study brochure and ask them if they are willing to discuss study participation with a member of the study staff. If they are, a member of the staff will contact them at the C&P office, if feasible, or by phone.

2. Consent: Voluntary informed consent will be obtained from all Veterans prior to participation. Consent will be obtained by one of the investigators or his/her designee after the research procedures and risks associated with participation have been explained to the candidate. A signed copy of the consent form will be provided to all potential Veterans.

Participants will be asked several questions to be certain they understand the risks associated with study participation. Only participants who correctly answer all the questions (with a second chance to answer questions if incorrectly answered the first time) will be enrolled. The questions will be the following:

a. What topics will you be asked about?

Answer should mention working.

b. Is it possible that someone will learn that you were at the study website?

The correct answer is "Yes."

c. Can you drop out of this study whenever you want? Yes.

B. Risks and Discomforts

Risks associated with participation in the study include risks associated with:

1. Completing questionnaires: Administration of study instruments may be boring, frustrating, or upsetting.

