been designed to avoid collecting identifiable information; no Protected Health Information (PHI) will be collected on study forms. We generally collect only protocol session dates. These dates are changed to ‘number of sessions completed’ when data sets are anonymized and released to other investigators. Research data, containing no PHI, will be uploaded to a secure VA server using SharePoint. SharePoint is a platform that allows users to create and share information, documents, and reports through a common secure VA intranet portal. Files containing audio-recorded sessions will be uploaded using SharePoint for rating at West Haven, after which they will be deleted. Data storage will use the HSR&D PRIME Center’s data storage servers (support letter attached).

Personal identifiers will be retained to obtain VA service use data. After the service use data has been extracted, the identifiers will be removed to create files with de-identified data for subsequent analyses. Source documents (e.g. Compensation and Pension examinations) are stored on VA clinical servers behind a secure firewall, and will not be stored with research data. Other forms that contain PHI such as consent forms will be collected by the two site PIs and stored in locked file cabinets by the site PI’s until seven years from the last study-regulated publication, unless VA regulations stipulate a different date and mode for their destruction.

All possible precautions will be taken to prevent a breach of confidentiality. Study IDs will be assigned at the time of recruitment and replace names and record numbers. Clinical enrollment records are kept separate from research data, and are not available without a Veteran’s written consent. Participants’ names will appear only on the consent form, HIPAA authorization form, and “key” form kept by the site P.I. All paper forms will be stored and secured in a locked file cabinet under the jurisdiction of the site P.I.

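### VA service use is collected around the Compensation examination and the claim decision, not randomization, so the baseline period can include weeks after assignment

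*Combined protocol and SAP*

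**What the plan says.** End of Study Measures, item 2 (VA Service Use Outcomes), is the only place that gives dates for this measure. Data run "from 24 weeks before the Compensation examination (to allow analyses to control for baseline service use) until 24 weeks after claims adjudication". The look-back is therefore tied to the examination and given a purpose, control for baseline use. The end is tied to the claim decision.

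Other sections use or list the measure without dates. The Schedule of Assessments has only an end-of-study entry, "VA Mental Health Service Use from VA Databases". Data Analysis 1.d (Process Measures) derives a number of weeks in treatment, with no counting period. Data Analysis 4 relates each potential mediator's slope to group and to the slope of hours worked, with no time origin for service use. Hypothesis 2A(iii) speaks of changes in weeks attended, without naming the two periods compared.

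On timing, section 6.A allows the baseline appointment before the "planned Compensation examination and up to 3 months after the exam". Randomization happens at website log-on, with a call after one week; then "If after one more week the Veteran has not been randomized, that participant will be discontinued from the study". The justification for letter recruitment (Human Subjects, A.1) adds that "assessments are designed to be collected before the Compensation examination".

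**The concern.** A baseline for a randomized comparison should end at randomization. Here it ends at the examination, and randomization before the examination is the intended route. For those Veterans the weeks between assignment and exam sit inside the period meant to represent baseline.

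Those weeks matter. The Background lists encouraging psychiatric treatment among the ways Benefits Counseling works, and the therapist starts calling in weeks 1 and 2. Early attendance after assignment is part of the effect sought, so treating it as baseline partly adjusts that effect away.

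The other end of the window has a related gap. Hours worked are followed to week 24 from randomization, but service use is followed to a date set by the claim decision, which differs between Veterans. At stake are the service-use outcome and mediator (iii) of Hypotheses 2A and 2B.

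**Working it through.** **Plan's own figure.** The plan gives no number for this measure. Its one precision figure, a 95% interval of (.01, .79) for a standardized slope difference of .40 with 52 per arm, can be reproduced: 0.40 ± 1.96 × √(2/52 + 0.40²/(4 × 52)) = 0.40 ± 1.96 × 0.1981 = (0.012, 0.788). No service-use quantity enters it.

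**Inputs.** Count weeks from the exam (week 0).
- Collection runs from −24 to A + 24, where A is the week of the claim decision (End of Study Measures, item 2). A is not given and is assumed below.
- The baseline visit is at week b. Section 6.A allows b up to 3 months, about 13 weeks, and sets no earliest limit. Values of b before the exam are assumed.
- Log-on delay D is 0 to about 2 weeks (section 6.A).
- Randomization is at r = b + D.

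**Formulas.**
- Post-randomization weeks inside the pre-exam look-back: E = −r if r is negative (at most 24), otherwise 0.
- Pre-randomization weeks collected: 24 + r, which is 24 − E when r is negative.
- Post-exam weeks before randomization: r if r is positive, otherwise 0.
- Post-randomization weeks collected: A + 24 − r, which is below 24 only when A is less than r.

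**Start of the window.**

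| Visit relative to exam | r | E | Pre-randomization weeks collected | Post-exam weeks before randomization |
|---|---|---|---|---|
| 8 weeks before (assumed) | −8 to −6 | 8 to 6 | 16 to 18 | 0 |
| 4 weeks before (assumed) | −4 to −2 | 4 to 2 | 20 to 22 | 0 |
| 2 weeks before (assumed) | −2 to 0 | 2 to 0 | 22 to 24 | 0 |
| Same day | 0 to 2 | 0 | 24 to 26 | 0 to 2 |
| 13 weeks after (latest allowed) | 13 to 15 | 0 | 37 to 39 | 13 to 15 |

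**Size of the dilution.** Suppose, for illustration, that counseling shifts weekly attendance by a constant amount from randomization on, and that change is follow-up rate minus the 24-week pre-exam rate. The baseline then absorbs E/24 of the shift, and the between-arm difference in change shrinks by the same share for the Veterans concerned: 2/24 = 8%, 4/24 = 17%, 8/24 = 33%. Veterans randomized on or after the exam contribute none of this.

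**End of the window.** With r = 15 and a decision 4 weeks after the exam (assumed), 4 + 24 − 15 = 13 post-randomization weeks are collected, short of week 24. With r = −8 and a decision at week 30 (assumed), the figure is 30 + 24 + 8 = 62.

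**The case against.** The best defense is that the protocol describes collection, not analysis. It does not say that all 24 pre-exam weeks form the baseline covariate, and an analyst could cut periods from randomization and discard surplus weeks. That stands in part. But the look-back is given a baseline purpose, no section says the data will be re-cut, and trimming cannot supply weeks that were not extracted.

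The amounts may also be small. Section 6.A explains its flexibility by noting that Veterans differ in their ability to "schedule appointments immediately before or after Compensation examinations", so short lead times may be common, and 20 weeks of prior use still gives a usable baseline rate. Coverage below 24 weeks after randomization is limited too. Veterans already receiving service connection are excluded, so this case mainly needs a denial, or a decision during the log-on interval. Following use after adjudication also has a rationale, since Module Three follows the decision. All of this stands, and it keeps the point minor.

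A reader might infer three stronger conclusions that the documents do not support.
- *The missing weeks are lost for good.* The plan says "After the service use data has been extracted, the identifiers will be removed to create files with de-identified data for subsequent analyses", but the same confidentiality section keeps a key form and a separately stored crosswalk file. Later re-linkage is not shown to be impossible.
- *Attendance counts are inflated for Veterans with late decisions.* That needs a raw total over the whole span. The plan describes changes and slopes and never specifies such a total.
- *The arms are biased against each other.* Eligibility requires a scheduled examination, log-on precedes knowledge of assignment, and an urn factor is "Current enrollment in VA psychiatric or substance abuse treatment (yes/no". Nothing suggests that timing would differ by arm.

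**Conclusion.** The point holds as a minor one. The only stated window for VA service use is tied to the examination and the claim decision. Followed as written, its baseline can include post-randomization weeks, with the same number of pre-randomization weeks not collected. With visits 2 to 8 weeks before the exam, that is 0 to 8 of the 24 weeks. In the other direction, up to about 15 post-exam weeks precede randomization. Coverage to week 24 fails only when the claim is decided before randomization.

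The lead times and decision dates are assumptions; that the two dates can differ comes from the plan. The expected effect is attenuation and noise, not a spurious difference between arms. It is confined to the service-use outcome and mediator (iii) of Hypotheses 2A and 2B, in an exploratory aim that the plan says is not powered for full mediation. Hours of paid work, their analysis and the precision calculation do not change.

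**What to change.** 1. Set the extract to cover at least randomization minus 24 weeks to randomization plus 24 weeks for every randomized Veteran, keeping the present span wherever it is wider.
2. Define baseline use as the 24 weeks before randomization.
3. Compute the mediator's change or slope over weeks 0 to 24 from randomization, to match hours worked. Four-week blocks (six in 24 weeks) are one convenient unit, but are optional.
4. Report use after week 24 separately as a service-use outcome. The follow-up after adjudication is then kept for its own purpose.

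The cost is different date limits in the same administrative extract and a few sentences in End of Study Measures and Data Analysis 1.d and 4. Veterans provide no new data. It is simplest to settle the limits before the extract is run.
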